### **5.6 Efficacy Evaluations (only if applicable)**

Not applicable.

## **5.7 Pharmacokinetic Evaluation (only if applicable)**

Not applicable.

## **5.8 Genetic Testing (only if applicable)**

The FAA CAMI plans to investigate changes in gene expression through RNA blood analyses. This analysis is exploratory in nature.

## **5.9 Safety Evaluation (only if applicable)**

Not applicable.

## **6 Statistical Plan**

We will perform similar analyses for the secondary outcomes. We will adjust for multiple testing using the false discovery rate method making sure that we keep the family-wise type I error rate at 5%. Multiple exploratory genetics analyses may be performed by FAA CAMI.

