#### 1.1 Background and Relevant Literature

Undisturbed sleep of sufficient duration and quality is of paramount importance for recuperation and health. Aircraft noise has been shown to disturb sleep and be associated with long-term health consequences like cardiovascular disease. While sound insulation can lower noise levels in the bedroom, it is expensive and only residents living close to the airport are eligible for compensation for sound insulation. Furthermore, residents often fail to close windows during the night to increase ventilation and decrease bedroom temperatures, which renders the sound insulation measures ineffective. Therefore, the identification of inexpensive and effective interventions to reduce the adverse effects of aviation noise on sleep is warranted.

Broadband noise (BN) is a promising and inexpensive intervention that could help mitigate the negative effects of aviation noise on sleep for large parts of the population that are either ineligible for sound insulation or still suffering from aviation noise-induced sleep disturbance despite sound insulation. This study will be the first to investigate – using the gold standard measure of sleep, polysomnography – the effectiveness of BN in mitigating the sleep-disturbing effects of aviation noise. Machines and apps that produce BN (e.g., white noise) are very popular (>200 different sound masking apps exist that have been downloaded >10 million times), but according to our own systematic review of the literature rigorous studies corroborating the sleep promoting effects of BN are missing. Also, as continuous BN exposure during the night could affect hearing, it will be important to assess temporary hearing threshold shifts after BN exposure nights.

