### **2.2 Secondary Objectives (if applicable)**

- To investigate the effects of the different noise conditions (see 3.1) on next day cognitive and driving simulator performance, gene expression in the blood, hearing thresholds, and subjective well-being.
- To investigate in an event-related analysis whether the different sources of aviation noise (e.g., jet engine, helicopter, drone, low sonic boom), at the same maximum sound pressure levels, differ in their potential to arouse subjects from sleep, and whether BN and EP differ in their potential to mitigate the arousing effects of the different kinds of aviation noise on sleep.
- To investigate to what degree BN and EP prevent arousal to meaningful sounds like alarms or a crying baby.

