### **Hearing Test**

We will perform a pure-tone audiometry using the Békésy technique preceded by a tympanometry during the first screening session as well as each evening and morning of the study. We will administer the test with a headphone system.

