### **3.4.2 Secondary Study Endpoints**

We plan to investigate the following secondary endpoints in relation to the different noise exposure conditions.

Sleep-related secondary endpoints:

1. Time spent awake and in different sleep stages (N1, N2, N3, REM)
2. Sleep fragmentation, i.e. number of awakenings and EEG arousals per hour sleep
3. Latency to sleep stages N2, N3 and REM
4. Frequency, density and amplitude of sleep spindles, K-complexes and vertex sharp waves
5. Power-spectral density in alpha, beta, theta and delta frequency bands
6. Event-related analysis with the following endpoints
  - a. Awakening
  - b. EEG arousal
  - c. Odds Ratio Product (ORP)

Non-sleep-related secondary endpoints:

1. Cognition test battery performance
  - a. One standard speed and one standard accuracy outcome for each of the 10 tests
  - b. Accuracy, speed and efficiency across cognitive domains
2. Driving simulator performance
  - a. Standard deviation of lateral position (i.e., continuous location of a vehicle with respect to a lane reference)
  - b. Standard deviation of speed
3. Hearing test
  - a. Threshold shift in dB at the following frequencies: 500 Hz, 1,000 Hz, 2,000 Hz, 4,000 Hz, 6,000 Hz, and 8,000 Hz
4. Blood test
  - a. Change in RNA expression levels

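### Overnight hearing shift, a harm the protocol itself attributes to broadband noise, is analysed as an ordinary secondary outcome behind an omnibus gate and a multiplicity adjustment, with no planned interval-based safety analysis

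*Combined protocol and SAP*

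**What the plan says.** **The harm.** Protocol section 1.1: "as continuous BN exposure during the night could affect hearing, it will be important to assess temporary hearing threshold shifts after BN exposure nights". Audiometry is done "during the first screening session as well as each evening and morning of the study" (section 3.3, Hearing Test), so an evening-to-morning change is available for every condition.

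**Its place in the plan.** Section 3.4.2, under the non-sleep secondary endpoints: "Threshold shift in dB at the following frequencies: 500 Hz, 1,000 Hz, 2,000 Hz, 4,000 Hz, 6,000 Hz, and 8,000 Hz". It stands beside cognition, driving and RNA expression.

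**Its analysis.** Section 6: "We will perform similar analyses for the secondary outcomes". Section 6.2 supplies the template: a mixed model, an omnibus test at 0.05 across the six conditions and, only if that is significant, all pairwise contrasts. Section 6 then adds "We will adjust for multiple testing using the false discovery rate method", "making sure that we keep the family-wise type I error rate at 5" per cent. No family is defined and no outcome is exempted.

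**What else covers hearing.** Section 5.9 (Safety Evaluation) is marked not applicable, and the numbered risks in section 10.1 do not mention hearing. Power is stated only for the primary sleep outcome (sections 6.1 and 6.2). There is no relevant shift in dB, no margin and no confidence-interval rule.

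**A second possible harm.** Section 2.2 has the objective "To investigate to what degree BN and EP prevent arousal to meaningful sounds like alarms or a crying baby". The event-related endpoints in section 3.4.2 do not separate these sounds from the aviation noise events.

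**The concern.** Multiplicity adjustment guards against false positive claims, which is what one wants for claims of benefit. For a harm the costly error is the opposite one, missing a real effect, and adjustment makes that error more likely. The omnibus gate adds a further hurdle: if the six-condition test is not significant, the contrasts of BN nights with nights without BN are not planned at all.

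Section 1.1 presents BN as an inexpensive option for large parts of the population, so the hearing result will be looked at for reassurance. The plan specifies only tests of no difference for it. If nothing is flagged, a reader has a p-value, weakened by adjustment, and no planned estimate to set against a shift that would matter.

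**Working it through.** **Inputs from the documents.** N = 24, each subject receiving all six conditions; two-sided alpha 0.05; effect size 0.60; primary contrast equivalent to a paired t-test (sections 6.1, 6.2 and 6.3.2).

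**Assumptions, because the documents give no figure.** The 0.60 is in units of the SD of the within-subject difference. The same standardised shift is used for hearing. Family size and the number of other real effects are varied.

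**1. The plan's own power.** Non-centrality 0.60 × √24 = 2.94 with 23 degrees of freedom; critical t = 2.069. Power = 80.4%, which agrees with the stated figure of at least 80%. This is also the unadjusted power for a 0.6 SD hearing shift at one frequency.

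**2. Size of the largest natural family.** From section 3.4.2, leaving out RNA:
- Sleep: 5 stage times + 2 fragmentation + 3 latencies + 9 (three features of three waveforms) + 4 spectral bands + 3 event-related = 26.
- Cognition: 10 × 2 + 3 = 23.
- Driving 2, hearing 6.
- Total: 26 + 23 + 2 + 6 = 57.

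**3. Strict family-wise reading (Bonferroni).** Same formula at alpha/m:
- m = 6: 53%.
- m = 57: 23%.

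**4. False-discovery-rate reading (Benjamini-Hochberg at 5%).** Simulation with 20,000 runs and one paired test per outcome. Other real effects are also 0.6 SD, and tests are independent unless noted.

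| Family | Real effects | Detection per shifted frequency |
|---|---|---|
| None (unadjusted) | – | 80% |
| 6 hearing tests | all six, independent | 77% |
| 6 hearing tests | all six, correlation 0.5 | 75% |
| 6 hearing tests | one frequency | 53% |
| 57 outcomes | one frequency + 25 others | 62% |
| 57 outcomes | one frequency + 10 others | 45% |
| 57 outcomes | one frequency only | 24% |

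Every adjusted case is below 80%. These runs do not include the omnibus gate or the 15 possible contrasts per outcome (6 × 5 / 2).

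**5. The omnibus gate by itself.** F test with 5 and 115 degrees of freedom, equal variances and correlations assumed. If one of the six conditions is shifted by 0.6 SD, non-centrality is 24 × 0.30 / 0.5 = 14.4 and the gate opens 83% of the time. If two are shifted, it is 24 × 0.48 / 0.5 = 23.0 and the gate opens 97% of the time. The gate matters less than a large adjusted family.

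**6. What non-significance would mean.** Even unadjusted, a true 0.4 SD shift is missed 53% of the time and a 0.3 SD shift 71%.

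**7. What an interval would give.** 95% half-width = 2.069 × SD / √24 = 0.42 SD. For an assumed SD of 3, 5 or 7 dB this is 1.3, 2.1 or 3.0 dB. The trial can produce an informative interval without more data.

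**The case against.** **The size is uncertain.** This stands. One family per outcome domain fits the text as well as one family of 57, and with six hearing tests, all shifted, the loss is only 3 to 5 percentage points. The low figures need a large family, a shift at a single frequency and few other real effects. Section 6 also names a false-discovery-rate method and family-wise control together, so neither reading can be excluded.

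**More endpoints need not mean less chance of a flag.** A reader might infer that each added sleep or cognition endpoint makes a hearing flag less likely. Under Benjamini-Hochberg that is false when the added endpoints are truly affected: with one frequency shifted, adding 25 real effects to the six hearing tests raises detection from 53% to 74%. If the 25 added endpoints are all null it falls to 31%. What holds is only that adjusted detection stays below unadjusted detection.

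**The plan never equates non-significance with safety.** A reader might infer that it will, or that the trial will go on to recommend 50 dBA. The documents say neither. Mixed models yield estimates and intervals, and nothing bars reporting them. The fair statement is that the plan does not require them and leaves the misreading open.

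**Adverse event reporting exists.** Section 7.1.1 would capture an abnormal test result judged clinically significant. That works subject by subject, without a dB criterion, and does not estimate a group shift.

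**Hearing is a stated research objective, and exempting harms from adjustment is partly convention.** Both are true. But section 1.1 gives possible harm as the reason for measuring it.

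**Conclusion.** The concern holds in limited form. A harm named in the protocol goes through the omnibus gate and the multiplicity adjustment like any other secondary outcome, and no estimate-based safety analysis is planned. That this makes a real shift harder to flag is certain in direction for any adjusted family larger than one test. The size is not fixed: for a 0.6 SD shift at 24 subjects, per-frequency detection falls from 80% to somewhere between about 77% and 23%. Where it lands depends on the undefined family, on which error rate is meant, and on how many other effects are real. The figures assume paired tests and an effect size borrowed from the primary outcome.

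For responses to alarm and baby-cry sounds the same reasoning applies in principle. The documents give no event counts or expected effects, so no power figure is claimed for them. This is a cheap improvement to the plan and does not bear on the primary analysis.

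**What to change.** In section 6:

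1. Label the six hearing endpoints as harm outcomes, outside the omnibus gate and the adjusted family.
2. Report the evening-to-morning shift at each frequency for BN50 against CTRL, AN+BN40 against AN, and AN+BN50 against AN, with unadjusted two-sided 95% confidence intervals.
3. State that a non-significant result is not evidence of no shift.
4. Allow a conclusion of no relevant shift only where the confidence interval lies below a margin in dB that is justified and fixed before analysis. Apply it at each frequency, not only to a six-frequency average, which would dilute a shift confined to one frequency.
5. Report the unadjusted difference in response probability to the alarm and baby-cry sounds, with its confidence interval.

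Items 1 to 3 and 5 are wording, with no new data or procedures. Item 4 needs a reasoned margin, which the documents do not supply. The price is a few more nominal hearing flags, which is acceptable for a harm outcome.

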### **6.1 Sample Size and Power Determination**

Power calculations were conducted using PASS (Version 21 NCSS), assuming a 5% type I error rate and using two-sided hypothesis tests. We used data collected in the AIRORA study performed at DLR to inform power calculations. With a proposed sample size of 24 subjects, we expect to have at least 80% power to detect a medium effect size of 0.60 for the mitigation effect of BN on our primary outcome due to aviation noise.

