### **6.2 Statistical Methods**

The primary outcome of the study is: time spent in slow wave sleep (SWS) plus rapid eye movement (REM) sleep during an 8-hour sleep opportunity (11 pm – 7 am). We will use linear mixed effect regression models with random subject intercept to investigate whether SWS+REM duration differs significantly between the 6 study conditions (we will use non-linear mixed effect models for binary secondary outcomes). If  $p < 0.05$  of the omnibus test, we will perform post-hoc tests contrasting all conditions with each other. Our primary contrast of interest for which the study was powered is the difference in SWS+REM duration in aviation noise nights with and without broadband noise of 50 dB.

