#### **6.3.2 Analysis of Primary Outcome of Interest**

Our primary contrast of interest is the difference in SWS+REM duration in aviation noise nights with and without broadband noise of 50 dB. In the mixed model framework, this is equivalent to a paired t-test.

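### The plan claims that a false discovery rate method keeps family-wise error at 5%, a guarantee the method does not give here, and does not say which tests the rule covers

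*Combined protocol and SAP*

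**What the plan says.** The section 6 preamble has two relevant sentences. The first is "We will perform similar analyses for the secondary outcomes". The next says the team will "adjust for multiple testing using the false discovery rate method making sure that we keep the family-wise type I error rate at 5" per cent. No FDR procedure is named, no family of tests is defined, and the second sentence is not limited to secondary outcomes.

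Section 3.4.2 introduces its list with "We plan to investigate the following secondary endpoints in relation to the different noise exposure conditions". The list is long; the cognition item alone calls for "One standard speed and one standard accuracy outcome for each of the 10 tests".

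For the primary endpoint (SWS+REM duration), section 6.2 fits a mixed model to the six conditions. If p is below 0.05 "of the omnibus test, we will perform post-hoc tests contrasting all conditions with each other". It then adds: "Our primary contrast of interest for which the study was powered is the difference in SWS+REM duration in aviation noise nights", with and without 50 dB broadband noise. Section 6.3.2 repeats that contrast and says "In the mixed model framework, this is equivalent to a paired t-test". Section 6.1 states that with 24 subjects, two-sided 5%, "we expect to have at least 80% power to detect a medium effect size of 0.60 for the mitigation effect of BN" on the primary outcome.

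Section 2.1 puts three countermeasures in the primary objective: broadband noise at two levels, and earplugs.

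**The concern.** FDR is the expected share of rejections that are false. The family-wise rate is the chance of one or more false rejections. Controlling the first at 5% does not control the second at 5% once some effects are real and several true nulls remain.

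Two things are at stake. A reader of a significant hearing, driving or cognition result would credit it with a 5% family-wise guarantee that the method does not supply. On the primary endpoint, the 40 dB and earplug contrasts belong to the primary objective, yet the plan does not say what error control they have or whether the preamble reaches them. Nor does it say whether the designated 50 dB contrast must wait for the omnibus test.

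**Working it through.** Conditions are abbreviated as in section 3.1: CTRL, AN (aviation noise), BN50 (50 dB broadband noise alone), AN+EP (earplugs), AN+BN40, AN+BN50.

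**1. The plan's own figure.** Inputs from sections 6.1 and 6.3.2: n = 24, effect 0.60 (read as mean difference over SD of differences), two-sided 5%, paired t. Noncentrality = 0.60 × √24 = 2.94; critical t on 23 df = 2.07; power = 80.4%. With mixed-model df of 5 × 23 = 115, power is 83.0%. The stated figure reproduces when the contrast is tested alone at 5%.

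**2. Why the two rates part.** Let V be false rejections and R all rejections. FDR = E[V / max(R, 1)]; family-wise error = P(V ≥ 1). If every null is true, V = R and the two are equal. If some rejections are correct, V/R is below 1 whenever V ≥ 1 and R > V, so family-wise error can exceed FDR.

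**3. Secondary endpoints.** Count from section 3.4.2, RNA excluded:
- sleep: 5 times awake or in stage + 2 fragmentation + 3 latencies + 9 (three features × three waveforms) + 4 spectral bands + 3 event-related = 26
- non-sleep: 20 cognition (10 × 2) + 3 across domains + 2 driving + 6 hearing = 31
- total: 26 + 31 = 57

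Benjamini-Hochberg (BH) rejects the k smallest p-values, with k the largest index for which p(k) ≤ 0.05 × k/57.

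Hand check with independent endpoints. If 14 real effects are always detected, any true-null p-value below 0.05 × 15/57 = 0.0132 is rejected. With 43 true nulls, the chance of at least one is 1 − (1 − 0.0132)^43 = 43%. With 6 real effects the bar is 0.05 × 7/57 = 0.0061, and 1 − (1 − 0.0061)^51 = 27%.

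Simulation: 24 subjects × 6 nights, residual SD 1, F test on 5 and 115 df for each endpoint, BH at 5%. In affected endpoints CTRL equals BN50 and the four AN nights are equally worse. An effect of 0.85 residual SD corresponds to the plan's 0.60, since 0.60 × √2 = 0.85.

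| Endpoints affected | Noise effect (residual SD) | Chance of any false endpoint, correlation 0.6 to 0 |
|---|---|---|
| 0 | – | 4-5% |
| 2 | 0.85 | 5-12% |
| 6 | 0.85 | 12-24% |
| 14 | 0.85 | 19-41% |
| 14 | 0.4 | about 7-9% |

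FDR itself stays at or below about 5% throughout.

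**4. Post-hoc contrasts on the primary endpoint.** Six conditions give 6 × 5/2 = 15 pairs. The simulation uses the same 24 × 6 layout, with the omnibus test at 5% as gate, then all pairs. It assumes independent residuals and no period or carry-over effects.

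| Pattern | Pairs truly equal | Any false pair, unadjusted | Any false pair, BH over 15 |
|---|---|---|---|
| No differences at all | 15 | 5% | 4% |
| Noise harmful (0.6-1.5 SD), BN50 = CTRL, no countermeasure works | 7 | 22-24% | 8-16% |
| Noise 1.0 SD; BN40 and earplugs half as effective as BN50 | 2 | 10% | 4% |
| Noise 1.0 SD; BN50 and earplugs work, BN40 inert, BN50 alone mildly harmful | 1 | 5% | 2% |

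In the second row, the seven equal pairs are CTRL–BN50 plus the six pairs among the four AN nights. The unadjusted column applies if the preamble does not cover these tests, the BH column if it does.

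**5. The designated contrast.** Tested alone, AN+BN50 versus AN has 5% error. Behind the omnibus gate, its mixed-model power is 75-83%, depending on the other conditions, against 83% ungated.

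**The case against.** **Scope.** The preamble opens the whole of section 6 and its multiplicity sentence carries no restriction. All-pairs testing is the plainest multiple testing in the plan, so the sentence may well be meant to cover it. This stands. A reader might infer from section 6.2 that the 15 contrasts are simply unadjusted, but the documents do not support so firm a statement. What they support is that coverage is not stated.

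**Generality.** A reader might infer that family-wise error exceeds 5% as soon as any effect is real. That is too broad. With one true null left, BH stays at about 5% or less, and few or weak effects cause little inflation. The correct statement is that 5% is not guaranteed.

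**Size.** With 28 endpoints affected at 0.85 SD, the simulation gives 26-50%. That needs all 26 sleep endpoints plus two others to be affected, with the top of the range at zero correlation. Section 10.1 does not anticipate major daytime symptoms, and zero correlation is implausible for sleep-stage times within a fixed 8-hour window. That case should not be used as the measure.

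**Model fit.** BH and one Gaussian omnibus test per endpoint are assumptions. Section 6.2 assigns binary outcomes to non-linear mixed models, and event-related endpoints rest on noise events described for the AN nights. The figures illustrate the defect and do not measure this trial. The contradiction between method and claim does not depend on them.

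**Conclusion.** The section 6 sentence is wrong as written. No reading of its scope makes an FDR method guarantee 5% family-wise error in a study that expects real noise effects. On the secondary list the excess runs from slight (about 7-9% with 14 weak effects) to substantial (19-41% with 14 effects at 0.85 SD), given BH, 57 endpoints and one omnibus test each. For the post-hoc contrasts the 5% claim fails on either reading in the pattern where noise is harmful and nothing mitigates it, and some other patterns show no inflation.

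A reader might conclude that the trial's main test is compromised. It is not: AN+BN50 versus AN, tested once at two-sided 5%, keeps its error rate and its stated power. This should be fixed, but it does not threaten the design.

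**What to change.** 1. **Section 6 preamble: make method and error rate agree.** Either delete the family-wise clause and state that FDR is controlled at 5%, naming the procedure and the family; or keep the family-wise claim and replace FDR with a procedure that delivers it, such as Holm. The choice is the sponsor's. The first option is wording only. The second costs power on the secondary outcomes, by an amount not calculated here.

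2. **Section 6.2: state whether that rule covers the post-hoc contrasts**, naming AN+BN40 versus AN and AN+EP versus AN, and make no family-wise claim for them under FDR. Adjustment costs power. For a 0.85 SD earplug effect, power is 83% unadjusted, 69-75% with gated BH over 15, 69% with Holm over four contrasts (AN+BN40 and AN+EP versus AN, AN and BN50 versus CTRL), and 52-56% with Holm over the 14 pairs other than the designated one. Holm over four is not clearly better than BH for the countermeasures; its gain is a true family-wise statement within its family.

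3. **Sections 6.2 and 6.3.2: state that AN+BN50 versus AN is tested once at two-sided 5%, outside the omnibus gate and the post-hoc family.** This matches section 6.1. If the plan now intends that contrast to sit behind the gate, this changes the test and is not merely wording.

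None of these changes alters the sample size or data collection.
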